6.4. General conventions and/or calculated variables

6.4.1. Subject reference start/end dates

For each subject, the reference dates will be the following:

- The reference start date is the date of inclusion visit.
- The reference end date is the date when subject was determined to have ended the trial.

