11.2. Adverse events

Note: in the following paragraph, for a smoother reading:

- Incidents and adverse events will be referred as adverse events (AE);
- treatment-emergent incidents and adverse events will be referred as treatment-emergent adverse event (TEAE).

AE are coded using the MedDRA dictionary version 25.0. They are classified by System Organ Class and Preferred Term.

An AE will be considered as a TEAE if:

- it was not present prior to the reference start date
- it was present prior to the reference start date and worsened during the study (increase of intensity)
- it reappears after the reference start date (finished before the reference end date)

A given TEAE (according to the MedDRA terminology) will be counted only once per subject. If a subject experienced several AEs in the same SOC/PT, the most severe intensity will be retained for this SOC/PT.

Note: if the intensity/severity is missing, a conservative approach will be adopted and the intensity/severity will be considered as severe.

Missing or incomplete dates will be estimated as described in section §6.4.4 in order to determine the TEAEs, but they will be presented as reported in CRF in the data listings. Generally, an AE for which the onset date is missing or incomplete and does not permit to identify the onset according to the date of the reference start date (i.e. missing onset day and month/year corresponding to the reference start date) will be considered as treatment-emergent.

Tables will present separately:

- **incidents related to the use of the medical device** (described as possibly related, probably related or related with the device in the eCRF),
- **adverse events not related to the use of the medical device**

- Summary of adverse-events

Summary tables will be produced for AEs not related to the use of medical device and for incidents related to the use of the medical device. Tables will be adapted depending on the definition of the type of AE

- number and percentage of subjects with at least one adverse event (AE)
- number and percentage of subjects with at least one AE leading to definitive study device discontinuation
- number and percentage of subjects with at least one AE leading to definitive study discontinuation
- number and percentage of subjects with at least one serious adverse event (SAE)
- number and percentage of subjects with at least one TEAE
 - number and percentage of subjects with one TEAE
 - number and percentage of subjects with two TEAE

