 - number and percentage of subjects with at least three TEAE

- Analysis of treatment-emergent adverse event

Only TEAE will be summarised by System Organ Class and Preferred term. The following tables will be provided:

- number and percentage of subjects with TEAE for AEs related to the chronic rhino sinusitis,
- number and percentage of subjects with TEAE for AEs related to the sino-nasal swab procedure,
- number and percentage of subjects with TEAE for incidents related to the use of the medical device

- Analysis of deaths, other serious adverse events and other significant adverse events

A listing of deaths will be provided if applicable.

A listing of serious adverse events will be also provided if applicable.

All AEs leading to definitive discontinuation of the trial device or definitive discontinuation of the trial will be listed if applicable.

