13. APPENDICES

13.1. Treatment emergent adverse events

AE: Adverse event / TEAE: Treatment emergent adverse event

Onset day = AE start date – Date of reference start date

Onset day (bis) = AE start date – Date of reference end date

D0 \rightarrow Onset day = 0

Figure 2 : Treatment emergent adverse events

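### The third TEAE criterion does not say which episode must have finished, and its natural reading drops same-intensity recurrences unresolved before trial end

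*SAP*

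**What the plan says.** SAP 11.2 gives three alternative routes to treatment-emergent status:

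1. "it was not present prior to the reference start date"
2. "it was present prior to the reference start date and worsened during the study (increase of intensity"
3. "it reappears after the reference start date (finished before the reference end date"

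SAP 6.4.1 fixes both dates: "The reference start date is the date of inclusion visit", and "The reference end date is the date when subject was determined to have ended the trial". For a completer these are Visit 1 (Day 1) and, presumably, Visit 2 (Day 30 ± 5).

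The classification decides what is tabulated: "Only TEAE will be summarised by System Organ Class and Preferred term". Protocol section 9 restricts the summaries in the same way. One summary row in SAP 11.2 does not depend on the classification: "number and percentage of subjects with at least one adverse event (AE".

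SAP 13.1 holds the figure that illustrates treatment emergence. The figure is not visible in the text available, but its legend is: "Onset day = AE start date – Date of reference start date", with a second onset day that sets the event's start date against the reference end date. The legend does not use the event's end date.

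**The concern.** The third criterion should catch an event that was over and then came back during the study. Its bracket adds a condition tied to the end of the trial without naming the episode it applies to. Grammatically, the nearest subject is the event that reappears. Read that way, a recurrence qualifies only if it resolves before the subject leaves the study. Short recurrences are then counted and unresolved ones of the same intensity are not.

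This would run against the rest of SAP 11.2, which is otherwise cautious: missing intensity is treated as severe, and an onset that cannot be placed relative to inclusion defaults to treatment-emergent.

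What is at stake is the content of Tables 14.3.2.3 to 14.3.2.6, and the treatment-emergent rows of the two brief summaries, in a study where systemic and local tolerance is a secondary objective. Subjects have had symptoms for at least 12 weeks (protocol 8.3), so the return of a past symptom is a foreseeable case. Two programmers could classify the same subject differently.

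**Working it through.** The plan states no figure for this rule, so there is none to reproduce. The check applies the three criteria to test events under each plausible reading.

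**Inputs.** Reference start Day 1 and reference end Day 30 (SAP 3 and 6.4.1). The earlier episode is over before Day 1 and the recurrence starts on Day 10. SAP 6.4.4 sets a completely missing end date of a non-ongoing event to the reference end date, and SAP 11.2 uses these estimated dates to determine treatment emergence.

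**Readings.**
- R1: the recurrence must have finished; criterion 1 is judged on the event's history.
- R2: as R1, but criterion 1 is judged on the onset of the new adverse-event record.
- R3: the earlier episode must have finished, with the end date as written.
- R4: the earlier episode must have finished before the reference *start* date (the presumed intention).

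| Event | R1 | R2 | R3 | R4 |
|---|---|---|---|---|
| Recurs, same intensity, ends Day 20 | yes | yes | yes | yes |
| Recurs, same intensity, ongoing at Visit 2 | **no** | yes | yes | yes |
| Recurs, same intensity, ends Day 30 | **no** | yes | yes | yes |
| Recurs, same intensity, not ongoing, end date missing (imputed Day 30) | **no** | yes | yes | yes |
| Recurs, worse than before, ongoing at Visit 2 | yes | yes | yes | yes |
| New event, ongoing at Visit 2 | yes | yes | yes | yes |

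(yes = treatment-emergent)

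**Why R1 fails the second row.** Criterion 1 fails because the event was present before. Criterion 2 fails because it did not worsen. Criterion 3 fails because it had not finished. In the third and fourth rows the end date equals the reference end date, so it is not before it.

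**What the other readings leave behind.** Under R2, every recurrence starting after Visit 1 already meets criterion 1, so criterion 3 is redundant. Under R3, an episode that reappears during the trial has necessarily ended before the trial ends, so the bracket is always true. R4 is coherent but is not the text.

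**Scale.** One subject in a Safety Set of 20 is 1/20 = 5.0 percentage points. The SAP's 20 is the target for completers without major deviation, so the Safety Set may differ: 1/18 = 5.6 points and 1/24 = 4.2 points. The chance of at least one such event among 20 subjects is 1 − (1 − p)^20, where p is the per-subject probability. The documents give no p. For assumed values of 1%, 5% and 10% the result is 18%, 64% and 88%.

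**The case against.** The strongest reply is that the exclusion needs two interpretive choices together: that the bracket describes the recurrence, and that criterion 1 looks at the subject's history rather than at the record being classified. Drop either and the recurrence is treatment-emergent. The SAP's mechanics lean towards onset: doubtful cases are settled by onset, and the SAP 13.1 legend uses start dates only. Past history is coded separately (SAP 8.3), so an episode resolved before Visit 1 could sit there while its return is entered as a new event. The bracket might also be a clumsy upper limit on the emergence window, and the figure may settle the matter.

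The consequences are limited too. An excluded event still counts in the any-adverse-event row and, where applicable, in the serious-event and discontinuation listings. Protocol section 9 promises a listing of all events. The only anticipated device effect is itching and irritation when treatment begins (protocol 6.2), which is not obviously a late, persisting recurrence.

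All of this stands as a limit on how firmly the exclusion can be asserted. It does not rescue the wording, because each reading that keeps the recurrence leaves either the bracket or the whole third criterion with nothing to do.

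**Conclusion.** Criterion 3 is wrong as written, at minor severity: it is an ambiguous operative rule whose natural reading misclassifies some events. Those are same-intensity recurrences that are ongoing at trial end, end on the last day, or have an end date imputed to that day.

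A reader might infer that every past event that recurs and is unresolved at Visit 2 is certainly lost. The documents do not support that. A recurrence of greater intensity qualifies under criterion 2 on any reading, and for the rest the outcome depends on which reading the programmer adopts. Nor do the documents show that the tolerance results are materially distorted. The number affected cannot be derived and may be zero. The figure of about 5 percentage points per subject assumes a Safety Set of about 20, and the test cases assume that a completer's reference end date is Visit 2.

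**What to change.** Reword criterion 3 along these lines: the event returns after the reference start date, its previous episode having ended before the return began, whether or not the return has resolved by the reference end date.

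Simply exchanging the end date for the start date in the bracket is not enough. An episode ongoing at Visit 1 that resolves during the study and then returns at the same intensity would not have finished before the start date, and so would be left out.

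Check that the figure in SAP 13.1 agrees with the new wording; whether it needs changing cannot be judged from the legend alone. Then look through the recorded events for recurrences ongoing at, or ending on, the reference end date, including imputed dates. If there are none, no table changes.

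The cost is one sentence and a short data check, with no new data collection. SAP section 12 already records a change to the adverse-event displays made after data review, so this clarification should be documented there in the same way.

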11.3. Concomitant treatments

Concomitant treatments are coded using the WHO-DRUG dictionary version 2022 Q1.

All treatments taken at least once after reference first date or appeared during the study will be summarised by Anatomical Therapeutic Class (ATC) and substance name. The number and percentage of subjects in each category will be computed.

Subjects will be counted only once within these ATC categories.

[figure not shown]
Note: a medication which began before the reference start date and is on-going after the reference start date is counted in “previous medications” (see §8.2) and in “concomitant medications”.

12. CHANGES IN THE CONDUCT OF THE STUDY OR PLANNED ANALYSIS

After data review, considering no serious adverse event related to the nasal swab occurred, display of AE is split between 2 categories “incident related to the study device” and “AE not related to the study device” instead of the former 3 categories (incident, AE related to nasal swab procedure and AE related to chronic rhinosinusitis).

13. APPENDICES

13.1. Treatment emergent adverse events

AE: Adverse event / TEAE: Treatment emergent adverse event

Onset day = AE start date – Date of reference start date

Onset day (bis) = AE start date – Date of reference end date

D0 \rightarrow Onset day = 0

Figure 2 : Treatment emergent adverse events

13.2. List of statistical tables, figures and listings

Type	Number	Title
STUDY SUBJECTS		
Table	14.1.1.1	Subjects disposition [Screened subjects]
Figure	14.1.1.1	Subjects disposition [Screened subjects]
Listing	14.1.1.1	Not included / excluded subjects – Reasons [Screened subjects]
Table	14.1.1.2	Summary of protocol deviations [Included subjects]
Listing	14.1.1.2	Subjects with at least one major protocol deviation [Included subjects]
Table	14.1.1.3	Premature withdrawal – Reason of withdrawal [Included subjects]
Listing	14.1.1.3	Subjects prematurely withdrawn [Included subjects]
DEMOGRAPHIC AND OTHER BASELINE CHARACTERISTICS		
Table	14.1.2.1	Baseline – Demographic Characteristics [FAS]
Table	14.1.2.2	Baseline – Medical and surgical past history [FAS]
Listing	14.1.2.2	Baseline – Subjects with a medical or surgical history [FAS]
Table	14.1.2.3	Baseline – Number (%) of subjects with at least one previous or concomitant medication, by WHO-Drug ATC class and substance name [FAS]
Table	14.1.2.4	Baseline - SNOT-22 Symptoms of chronic rhinosinusitis scores [FAS]
Table	14.1.2.5.1	Baseline – Baseline safety variables – Adverse events since enrolment [FAS]
Table	14.1.2.5.2	Baseline – Baseline safety variables – Serious Adverse events potentially related to the sino-nasal swab procedure [FAS]
Table	14.1.2.6	Baseline – Other baseline variables [FAS]
EFFICACY		
Table	14.2.1	Secondary efficacy criteria – SNOT-22 score [FAS]
Table	14.2.2	Secondary efficacy criteria – Subject satisfaction [FAS]
Table	14.2.3	Secondary efficacy criteria – Symptoms of chronic rhino sinusitis [FAS]
Table	14.2.4	Secondary efficacy criteria – Weight of device [FAS]
SAFETY		
Table	14.3.1.1	Safety – Study duration by subject [Safety Set]
Table	14.3.1.2	Safety – Summary of compliance [Safety Set]
Table	14.3.1.3	Safety – Concomitant treatments [Safety Set]
SAFETY – Adverse events		

Type	Number	Title
Table	14.3.2.1	Safety – Brief summary of incidents related to the use of the medical device [Safety Set]
Table	14.3.2.2	Safety – Brief summary of adverse events not related to the use of the medical device [Safety Set]
Table	14.3.2.3	Safety – TEAE (incidents) related to the use of the medical device by System Organ Class and preferred term [Safety Set]
Table	14.3.2.4	Safety – TEAE not related to the use of the medical device by System Organ Class and preferred term [Safety Set]
Table	14.3.2.5	Safety – Serious TEAE (incidents) related to the use of the medical device by System Organ Class and preferred term [Safety Set]
Table	14.3.2.6	Safety – Serious TEAE not related to the use of the medical device by System Organ Class and preferred term [Safety Set]

SUBJECTS DATA LISTINGS

[figure not shown]
Listing	16.2.1	Discontinued subjects
Listing	16.2.2	Protocol deviations
Listing	16.2.3	Subjects excluded from the efficacy analysis
Listing	16.2.4	Demographic data
Listing	16.2.5	Compliance data
Listing	16.2.6	Individual efficacy response data

13.3. Mock tables

Table 14.1.1.1. Subjects disposition [Screened subjects]

Healsea Chronic N=XX	
Analysis Sets	
Screened subjects	XX (100.0%)
Included subjects	XX (XX.X%)
Safety Set	XX (XX.X%)
Full Analysis Set	XX (XX.X%)
Per Protocol Set	XX (XX.X%)

Figure 14.1.1.1. Subjects disposition [Screened subjects]

Listing 14.1.1.1. Not included / excluded subjects – Reasons [Screened subjects]

ID – Sex – Age	Category	Inclusion / Exclusion criterion	Answer
	Inclusion Exclusion		No Yes

Table 14.1.1.2 Summary of protocol deviations [Included subjects]

Healsea Chronic N=XX	
Subjects with at least one protocol deviation	
All	XX (XX.X%)
Category of deviation	
Minor	XX (XX.X%)
Major	XX (XX.X%)

Listing 14.1.1.2 Subjects with at least one major protocol deviation [Included subjects]

ID – Sex – Age	Treatment	Safety Set	Full Analysis Set	Per-Protocol Set	Protocol deviation	Classification of deviation
	Healsea Chronic					
	Healsea Chronic					

Table 14.1.1.3. Premature withdrawal – Reason of withdrawal [Included subjects]

Healsea Chronic N=XX	
Reason of premature withdrawal	
XXXXXXX	XX (XX.X%)

Listing 14.1.1.3 Subjects prematurely withdrawn [Included subjects]

ID – Sex – Age	Treatment	Safety Set	Full Analysis Set	Per-Protocol Set	Reason of withdrawal
	Healsea Chronic				
	Healsea Chronic				

Table 14.1.2.1. Baseline - Demographic characteristics [FAS]

Healsea Chronic N=XX	
Age (years)	
N	XX
Missing	XX
Mean (SD)	XX.X (XX.X)
Median	XX
Q1/Q3	XX / XX
Min/Max	XX / XX
Sex	
N	XX
Missing	XX
Female	XX (XX.X%)
Male	XX (XX.X%)

Table 14.1.2.2. Baseline - Medical and surgical past history [FAS]

Healsea Chronic N=XX	
SOC - Preferred Term	
All	XX (XX.X%)
Subjects with at least one medical history	
All	XX (XX.X%)
XXXXX	XX (XX.X%)
All	XX (XX.X%)
XXXXX	XX (XX.X%)
XXXXX	XX (XX.X%)

Listing 14.1.2.2 Baseline – Subjects with a medical or surgical history [FAS]

ID – Sex – Age	Treatment	Safety Set	Full Analysis Set	SOC	Preferred term	Start date / end date
	Healsea Chronic					
	Healsea Chronic					

Table 14.1.2.3. Baseline – Number (%) of subjects with at least one previous or concomitant medication, by WHO-Drug ATC class and substance name [FAS]

Healsea Chronic N=XX	
ATC1 - ATC2	
All	XX (XX.X%)
Subjects with at least one previous medication	
All	XX (XX.X%)
XXXXX	XX (XX.X%)
All	XX (XX.X%)
XXXXX	XX (XX.X%)
XXXXX	XX (XX.X%)

Table 14.1.2.4. Baseline - SNOT-22 Symptoms of chronic rhinosinusitis scores [FAS]

Healsea Chronic N=XX	
XXXXX score	
N	XX
Missing	XX
Mean (SD)	XX.X (XX.X)
Median	XX
Q1/Q3	XX / XX
Min/Max	XX / XX
Total score	
N	XX
Missing	XX
Mean (SD)	XX.X (XX.X)
Median	XX
Q1/Q3	XX / XX
Min/Max	XX / XX

Table 14.1.2.5.1. Baseline – Baseline safety variables – Adverse events since enrolment [FAS]

		Healsea Chronic N=XX	
		n (%)	[E]
Number and percentage of subjects with / Number of			
Incident		XX (XX.X%)	XXX
Incident leading to definitive study device discontinuation		XX (XX.X%)	XXX
Serious incident		XX (XX.X%)	XXX

Table 14.1.2.5.2. Baseline – Baseline safety variables – Serious Adverse events potentially related to the sino-nasal swab procedure [FAS]

		Healsea Chronic N=XX	
		n (%)	[E]
Serious Adverse events potentially related to the sino-nasal swab procedure			
All		XX (XX.X%)	XXX
XXXXX			
All		XX (XX.X%)	XXX
XXXXX		XX (XX.X%)	XXX
XXXXX		XX (XX.X%)	XXX

Table 14.1.2.6. Baseline – Other baseline variables [FAS]

Healsea Chronic N=XX	
XXXX sino-nasal symptom	
N	XX
Missing	XX
Yes	XX (XX.X%)
No	XX (XX.X%)
N	XX
Missing	XX
Lasting for 12 weeks or longer	XX (XX.X%)
For less than 12 weeks	XX (XX.X%)
XXXX rhinologic examination	
N	XX
Missing	XX
Yes	XX (XX.X%)
No	XX (XX.X%)

Table 14.2.1. Secondary efficacy criteria - SNOT-22 score [FAS]

Healsea Chronic N=XX	
XXXXX score – End of Study	
N	XX
Missing	XX
Mean (SD)	XX.X (XX.X)
Median	XX
Q1/Q3	XX / XX
Min/Max	XX / XX
XXXXX score – Change from baseline	
N	XX
Missing	XX
Mean (SD)	XX.X (XX.X)
Median	XX
Q1/Q3	XX / XX
Min/Max	XX / XX
Total score – End of Study	
N	XX
Missing	XX
Mean (SD)	XX.X (XX.X)
Median	XX
Q1/Q3	XX / XX
Min/Max	XX / XX
Total score – Change from baseline	
N	XX
Missing	XX
Mean (SD)	XX.X (XX.X)
Median	XX
Q1/Q3	XX / XX
Min/Max	XX / XX

Table 14.2.2. Secondary efficacy criteria – Subjects satisfaction [FAS]

Healsea Chronic N=XX	
How would you characterize the use of Healsea Chronic nasal spray?	
N	XX
Missing	XX
0: not easy	XX (XX.X%)
1: pretty easy	XX (XX.X%)
2: easy	XX (XX.X%)
3: very easy	XX (XX.X%)
How would you characterize the residual taste after spraying Healsea Chronic?	
N	XX
Missing	XX
0: not pleasant	XX (XX.X%)
1: neutral	XX (XX.X%)
2: pleasant	XX (XX.X%)
3: very pleasant	XX (XX.X%)
How would you characterize the cleansing and moistening of nasal mucosa with Healsea Chronic?	
N	XX
Missing	XX
0: no improvement	XX (XX.X%)
1: slight improvement	XX (XX.X%)
2: moderate improvement	XX (XX.X%)
3: very clear improvement	XX (XX.X%)

Table 14.2.3. Secondary efficacy criteria – Symptoms of chronic rhinosinusitis [FAS]

Healsea Chronic N=XX	
XXXX sino-nasal symptom – End of study	
N	XX
Missing	XX
Yes	XX (XX.X%)
No	XX (XX.X%)
XXXX sino-nasal symptom – Change from baseline	
N	XX
Missing	XX
Improvement	XX (XX.X%)
No change – symptom present	XX (XX.X%)
No change – symptom absent	XX (XX.X%)
Degradation	XX (XX.X%)

Table 14.2.4. Safety - Secondary efficacy criteria – Weight of device [FAS]

Healsea Chronic N=XX	
Returned device	
N	XX
Missing	XX
Yes	XX (XX.X%)
No	XX (XX.X%)
Weight of returned device	
N	XX
Missing	XX
Mean (SD)	XX.X (XX.X)
Median	XX
Q1/Q3	XX / XX
Min/Max	XX / XX

Table 14.3.1.1. Safety - Study duration by subject [Safety Set]

Healsea Chronic N=XX	
Study duration (days)	
N	XX
Missing	XX
Mean (SD)	XX.X (XX.X)
Median	XX
Q1/Q3	XX / XX
Min/Max	XX / XX

Table 14.3.1.2. Safety - Summary of compliance [Safety Set]

Healsea Chronic N=XX	
Compliance (%)	
N	XX
Missing	XX
Mean (SD)	XX.X (XX.X)
Median	XX
Q1/Q3	XX / XX
Min/Max	XX / XX

Table 14.3.1.3. Safety – Concomitant treatments [Safety Set]

ATC1 - ATC2	Healsea Chronic N=XX
Subjects with at least one concomitant treatment	
All	XX (XX.X%)
XXXXXX	
All	XX (XX.X%)
XXXXX	XX (XX.X%)
XXXXX	XX (XX.X%)

Table 14.3.2.1 Safety – Brief summary of incidents related to the use of the medical device [Safety Set]

Number and percentage of subjects with related / Number of related	Healsea Chronic N=XX	
	n (%)	[E]
Incident	XX (XX.X%)	XXX
Incident leading to definitive study device discontinuation	XX (XX.X%)	XXX
Incident leading to definitive study discontinuation	XX (XX.X%)	XXX
Serious incident	XX (XX.X%)	XXX
At least one treatment-emergent incident	XX (XX.X%)	XXX
Exactly one treatment-emergent incident	XX (XX.X%)	XXX
Exactly two treatment-emergent incident	XX (XX.X%)	XXX
At least three treatment-emergent incidents	XX (XX.X%)	XXX

Table 14.3.2.2 Safety – Brief summary of adverse events not related to the use of the medical device [Safety Set]

		Healsea Chronic N=XX	
		n (%)	[E]
Number and percentage of subjects with related / Number of related			
Incident		XX (XX.X%)	XXX
Incident leading to definitive study device discontinuation		XX (XX.X%)	XXX
Incident leading to definitive study discontinuation		XX (XX.X%)	XXX
Serious incident		XX (XX.X%)	XXX
At least one treatment-emergent incident		XX (XX.X%)	XXX
Exactly one treatment-emergent incident		XX (XX.X%)	XXX
Exactly two treatment-emergent incident		XX (XX.X%)	XXX
At least three treatment-emergent incidents		XX (XX.X%)	XXX

Table 14.3.2.3. Safety – TEAE (incidents) related to the use of the medical device by System Organ Class and preferred term [Safety Set]

		Healsea Chronic N=XX	
		n (%)	[E]
Related treatment-emergent adverse events			
All		XX (XX.X%)	XXX
XXXXXX			
All		XX (XX.X%)	XXX
XXXXXX		XX (XX.X%)	XXX
XXXXXX		XX (XX.X%)	XXX

Table 14.3.2.4. Safety – TEAE not related to the use of the medical device by System Organ Class and preferred term [Safety Set]

		Healsea Chronic N=XX	
		n (%)	[E]
Related treatment-emergent adverse events			
All		XX (XX.X%)	XXX
XXXXXX			
All		XX (XX.X%)	XXX
XXXXXX		XX (XX.X%)	XXX
XXXXXX		XX (XX.X%)	XXX

Table 14.3.2.5. Safety – Serious TEAE (incidents) related to the use of the medical device by System Organ Class and preferred term [Safety Set]

		Healsea Chronic N=XX	
SOC - Preferred Term	n (%)	[E]	
Related treatment-emergent adverse events			
All	XX (XX.X%)	XXX	
XXXXX			
All	XX (XX.X%)	XXX	
XXXXX	XX (XX.X%)	XXX	
XXXXX	XX (XX.X%)	XXX	

Table 14.3.2.6. Safety – Serious TEAE not related to the use of the medical device by System Organ Class and preferred term [Safety Set]

		Healsea Chronic N=XX	
SOC - Preferred Term	n (%)	[E]	
Related treatment-emergent adverse events			
All	XX (XX.X%)	XXX	
XXXXX			
All	XX (XX.X%)	XXX	
XXXXX	XX (XX.X%)	XXX	
XXXXX	XX (XX.X%)	XXX	

